In general, neuraxial modalities such as thoracic epidural and para-vertebral injections/catheters are subject to a wide array of limitations, including patient coagulopathy (Internal Normalized Ratio > 1.5), co-existing spine fractures, peri-insertion and removal holding of venous thromboembolism pharmacoprophylaxis, and provider availability. For these reasons, our current practice is to insert a subscapular “pain catheter” at the conclusion of the SSRF operation (Figure 2); this catheter provides a continuous infusion of 0.25% bupivacaine and may be left in place for several days.

Although favorable results using the pain catheter have been published in patients with rib fractures who have not undergone SSRF (8), we have noticed several limitations to this treatment modality. First, position is highly variable; and, because the catheter is not truly in the space of the intercostal nerves (Figure 3), drug delivery is likely irregular. This variability may be particularly relevant in obese patients; and the median body mass index of patient who underwent SSRF at Denver Health is 29 kg/m². Beyond catheter placement, we have also experienced issues with leakage of drug from the skin entry site of the catheter. Moreover, catheters frequently become dislodged or inadvertently removed during patient transport. Further, the indwelling foreign body likely introduces some risk of infection. Finally, the presence of the catheter is distressing to many patients.

Liposomal bupivacaine (Exparel, Pacira Pharmaceuticals, Inc., Parsippany, NJ, www.pacira.com) provides sustained analgesia for up to 72 hours following a single injection of the drug delivery system. The safety and efficacy of liposomal bupivacaine has been evaluated

in over 1,300 subjects and 21 clinical trials (refs from pamphlet). Although many of these trials have included thoracic surgery patients (9-11), no trial has evaluated the efficacy and safety of liposomal bupivacaine administered to patients with rib fractures undergoing SSRF. Potential benefits as compared to current practice include directed injection into the intercostal nerve space using a VATS approach, as well as obviation of the need for an indwelling catheter. The hypothesis of the current clinical trial is that, among patients undergoing SSRF, liposomal bupivacaine delivered via VATS intercostal nerve block provides comparable analgesia to the pain catheter, as measured by both pulmonary function and narcotic use.

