III. Preliminary Studies/Progress Report:

Although SSRF is now a recognized treatment for patients with severe chest wall injuries, the method of loco-regional anesthesia is less standardized. Currently thoracic epidural and paravertebral catheters are both common methods for delivering loco-regional anesthesia. Thoracic epidural catheters offer the benefit of bilateral analgesia and have been shown to reduce the length of mechanical ventilation (3). Unfortunately they are contra-indicated in the setting of spine fractures and mild coagulopathy, and may require the addition of a consultative service to manage. Paravertebral pain catheters have equivalent pain control to epidural catheters, but can be used in patients with spine fractures and can be placed surgically or by emergency teams using anatomic landmarks or ultrasound guidance (3). Denver health has found that these catheters are not without issues for our patients. Some issues that we have personally experienced include drug leakage, dislodgement, and irregular drug delivery. Other pain loco-regional analgesic modalities such as intrapleural pain catheters, transcutaneous patches, transcutaneous electrical nerve stimulation, and acupuncture have limited evidence to support their use (3). While still a relatively new technique for loco-regional anesthesia, liposomal bupivacaine has shown favorable results in patients undergoing thoracoscopies and thoracotomies, resulting in shorter hospital length of stay (11) and statistically significant additional analgesics (10). The ease of delivery of liposomal bupivacaine and the ability to avoid bothersome catheters may make it the optimal method for loco-regional anesthesia in patients undergoing SSRF.

IV. Research Methods

A. Outcome Measure(s):

Individuals undergoing SSRF will be randomized to two treatment arms. Primary outcomes will be pulmonary function and narcotic requirement by each subject.

Pulmonary function will be measured using the Standardized Assessment of Respiratory Function (SCARF) score, measured at 10 am daily. This scale has 4 components, and one point award for each of the following:

- 1) Numeric Pain score >4 (on the 10 point pain scale)
- 2) Incentive spirometry <50% predicted
- 3) Poor cough
- 4) Respiratory rate ≥ 20

Daily Narcotic use will be measured using equi-analgesic doses as shown in the table below.

Narcotic	Dose	Unit	Route
Hydromorphone	1.5	Mg	IV
Hydromorphone	7.5	Mg	PO
Fentanyl	100	Mcg	IV
Morphine	10	Mg	IV

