Morphine	30	Mg	PO
Oxycodone (Percocet)	20	Mg	PO
Hydrocodone (Vicodin)	30	Mg	PO

B. Description of Population to be Enrolled:

Adults undergoing surgical stabilization for rib fractures are eligible for this clinical trial. Any individuals that are pregnant, incarcerated, less than 18 years old, or have a known allergy or hypersensitivity to bupivacaine will not be eligible for enrollment.

C. Study Design and Research Methods

This is a non-inferiority, randomized clinical trial that compares two different delivery options for loco-regional anesthesia for patients undergoing surgical stabilization of rib fractures. Randomization will be accomplished using a standard function in Microsoft Excel that randomly chooses either the number 0 or 1.

Prior to patient's SSRF procedure they will be localized to one of two study arms:

- 1) Pain Catheter: placed in the subscapular space at the time of surgery and results in a continuous infusion of 12ml/hr of 0.25 bupivacaine and is left in place for a maximum of 120 hours.
- 2) Single injection liposomal bupivacaine: a mixture of 20mL liposomal bupivacaine, 20 mL 0.25% bupivacaine, and 10mL sterile saline (50mL total) that is delivered into the intercostal space during VATS using a 22 gauge needle directed at ribs 3 through 8. (178mm????)

The SSRF procedure will be standardized for all patients to include: 1) flexible bronchoscopy, 2) E-Z Blocker bronchial blocker (figure 5), and 3) VATS evacuation/irrigation of the pleural space.

Postoperatively, standard multimodal analgesia will be used in all patients (barring any contra-indications) to include: 1) Acetominophen 650 mg PO q6H, 2) Ibuprophen 800 mg PO q6h, and 3) Gabapentin 300 mg PO TID

Subjects will be followed for 28 days or until discharged from the hospital, whichever comes first. Crossover from one study arm to the other will not be permitted. Patients in whom pain is not well controlled postoperatively will be given additional analgesics other than bupivacaine.

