Occasionally patients with rib fractures receive a pain catheter placed prior to surgery using anatomic landmarks. For these patients the presence of a pre-existing pain catheter will be noted in the data collection sheet. Patient's with a pre-existing pain catheter will have it removed at the time of SSRF. Depending on randomization status, the patient will receive either a new pain catheter placed intra-operatively and under direct vision, or liposomal bupivacaine administered via VATS intercostal nerve block.

D. Description, Risks and Justification of Procedures and Data Collection Tools:

On October 28th 2011, the Food and Drug Administration approved liposomal bupivacaine for the following indication: "administration into the surgical site to produce postsurgical analgesia".

This study will be conducted and reported in accordance with the recommendations of the Consolidated Standards of Reporting Trials Statement (14) and registered with the U.S. National Institutes of Health (clinicaltrials.gov). An independent study monitor ([name], Pharm D) will submit written reports to COMIRB every six months. Adverse events will be recorded and reported to both the data safety monitor and COMIRB.

E. Potential Scientific Problems:

This is a randomized, clinical trial, however, due to the nature of the two treatment arms this study is not blinded. Clinical providers, patients, and the research coordinator collecting data will know which treatment arm the patient is assigned to. This study is subject to the Hawthorne Effect in which the patients may modify their behavior while being observed. Specifically, patients may exaggerate or downplay their pain level while being enrolled. Reported pain, especially on the 10-point pain scale is also highly subjective and will be a limitation in this study. The SCARF

score also incorporates other variables, such as respiratory rate and incentive spirometry volumes which are less subject measures. These will help mitigate the subjectivity of self-reported pain scores.

F. Data Analysis Plan:

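### Follow-up ends at hospital discharge, so adverse events after discharge are not planned to be captured in either arm, and reported counts may cover unequal observation time

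*Combined protocol and SAP*

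**What the plan says.** Section IV.C (Study Design and Research Methods) sets one follow-up rule for everything: "Subjects will be followed for 28 days or until discharged from the hospital, whichever comes first". Section IV.D adds that "Adverse events will be recorded and reported to both the data safety monitor and COMIRB". It gives no adverse-event window, no list of events and no contact after discharge.

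Four other statements bear on the point:

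- Section II gives safety as part of the rationale: "no trial has evaluated the efficacy and safety of liposomal bupivacaine administered to patients with rib fractures undergoing SSRF".
- Section II also names a harm of the comparator: "Further, the indwelling foreign body likely introduces some risk of infection".
- Exposure lasts for days in both arms. Section II says the liposomal product "provides sustained analgesia for up to 72 hours following a single injection of the drug delivery system"; section IV.C says the catheter "is left in place for a maximum of 120 hours".
- Section III reports a shorter hospital stay with liposomal bupivacaine after thoracoscopy and thoracotomy. It does not give the size of the reduction.

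Section IV.F (Data Analysis Plan) names no safety endpoint. Its sentence on chi-squared and Fisher's tests covers categorical variables in general.

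**The concern.** Two things follow from ending follow-up at discharge.

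First, harms that show themselves at home or lead to readmission are not planned to be seen in either arm. Infection related to an indwelling catheter can appear after the catheter is out and the patient has left. Avoiding the catheter is one of the benefits claimed for the new technique, so the plan may fail to observe the harm it expects to reduce.

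Second, length of observation becomes something that happens after randomisation. If one arm goes home sooner, its adverse-event count covers fewer days, and a side-by-side table of counts no longer compares like with like.

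At stake is how complete and how comparable the reported adverse events are. The SCARF and narcotic outcomes are not part of this point.

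**Working it through.** The plan gives no figure for adverse-event capture, so there is none to reproduce. The sample size of 34 does not depend on the follow-up rule; it is used here only for the expected arm size, 34 / 2 = 17. **Length of stay, event rates and onset times below are assumptions.**

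**1. Share of 28-day events seen before discharge on day L.** Two onset patterns are assumed:

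- (a) uniform over 28 days: L / 28
- (b) early onset, exponential with mean 7 days, truncated at 28: (1 − e^(−L/7)) / (1 − e^(−4))

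| Discharge day | (a) uniform | (b) early onset |
|---|---|---|
| 5 | 18% | 52% |
| 7 | 25% | 64% |
| 10 | 36% | 77% |

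With an assumed true 28-day risk of 10%, 17 × 0.10 = 1.7 events are expected per arm. Discharge on day 5 would show 0.30 (a) or 0.88 (b) of them. This loss occurs even when stays are equal.

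**2. Unequal stays, equal true risk.** Assume discharge on day 5 (liposomal) and day 7 (catheter).

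- Ratio of captured shares, liposomal to catheter: 0.71 (a) or 0.81 (b); the true ratio is 1.00.
- Constant risk of 2% per day: 1 − 0.98^5 = 9.6% and 1 − 0.98^7 = 13.2%, ratio 0.73. For 1% to 5% per day the ratio is 0.72 to 0.75.
- Stays of 7 and 9 days, same range of daily risks: 0.79 to 0.82.
- In events at 2% per day: 17 × 0.096 = 1.6 against 17 × 0.132 = 2.2, a gap of about 0.6 of an event.

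This mechanism lowers the count in whichever arm leaves sooner.

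**3. A late harm in the catheter arm only.** Assume infection onset is exponential with a median of 10 days and discharge is on day 7. Share captured: 1 − 2^(−7/10) = 38%. Medians of 7 and 14 days give 50% and 29%. If the catheter truly added 10 percentage points of infection risk, the recorded excess would be 10 × 0.38 = 3.8 points (5.0 to 2.9 across those medians). In events, 17 × 0.10 = 1.7 would occur and 1.7 × 0.38 = 0.65 would be seen, so about 1.05 would be missed.

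This mechanism hides catheter harm and so favours the catheter.

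**4. Direction.** Steps 2 and 3 pull opposite ways if the liposomal arm leaves sooner, and are of similar order (about 0.6 and 1 event at 17 per arm). The documents supply nothing with which to net them.

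**5. Precision under any window.** Zero events in 17 patients gives a one-sided 95% upper limit of 1 − 0.05^(1/17) = 16%.

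**The case against.** The strongest reply is that this is a 34-patient analgesia trial whose hypothesis and primary outcomes are pulmonary function and narcotic use. No safety comparison is specified, every input to the illustration is assumed, and a shift of about 0.6 of an event would persuade nobody. Section IV.D sets no explicit cut-off for adverse events, and the data collection tool cited in section IV.F is not in the text available here. All of this limits the weight of the point. It does not remove it: section IV.C ends follow-up at discharge without exception, and nothing available extends it for adverse events.

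Three stronger readings are tempting, and the documents do not support them.

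- **That the rule favours liposomal bupivacaine.** This needs a shorter stay in that arm. The only support is one statement in section III about other operations. The one late harm the protocol names belongs to the catheter arm, and missing it would favour the catheter.
- **That patients will be discharged during the catheter period.** The 120 hours is a maximum, and nothing says a patient may go home with the infusion running. Nor is the 72 hours a risk window; it is a stated duration of analgesia. With no length of stay given, how often discharge would precede either time is unknown.
- **That the plan tests safety without allowing for days observed.** The categorical-test sentence in section IV.F is generic and does not mention adverse events.

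**Conclusion.** The concern holds in a limited form. Under section IV.C as written, harms after discharge are not planned to be captured in either arm, in a trial whose background says safety in this population is unevaluated. If stays differ by arm, the reported counts would also cover unequal time, and the direction of the resulting bias cannot be stated.

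That late events fall outside follow-up rests on the text alone. How many are lost rests wholly on assumptions: under the two onset patterns, discharge between days 5 and 10 would miss between 23% and 82% of 28-day events (100% − 77% and 100% − 18%). Unequal counts additionally require a difference in stay that the documents do not establish.

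The consequence is for adverse-event reporting. It does not undermine the primary analysis, but it is cheap to correct before enrolment.

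**What to change.** In section IV.C, separate the two windows:

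- Keep SCARF and narcotic collection in hospital, as now.
- Record adverse events, wound or pleural infection, readmission and death to a fixed day 28 for every patient, whether or not discharged. State the day from which the 28 days are counted.
- Collect these by chart review plus one call from the existing coordinator, using the same script in both arms.

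In section IV.F, state that adverse-event counts will be reported by arm over that common window, together with days in hospital by arm.

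The cost is a protocol amendment and one call plus one chart check for each of 34 patients, by existing staff. Sample size, randomisation, treatment and primary outcomes are unchanged. There are limits: some patients may not be reached, care at other hospitals may be missed, the coordinator knows the treatment arm (the common script reduces but does not remove that problem), and with 34 patients the safety estimates stay imprecise.

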Inferiority of liposomal bupivacaine as compared to pain catheter will be defined as median daily SCARF score one point higher. Standard deviation of the SCARF score among patients with rib fractures in Denver Health surgical intensive care unit is 1.1. Using beta = 0.80 and alpha = .05, this returns a total sample size of 34 subjects. Twenty-four SSRF procedures are performed annually at Denver Health, thus we conclude that the trial is feasible and may be completed in 1.5 years.

A standard data collection tool will be used (see Data Collection Tool). All statistical analysis will be conducted using SAS version 9.4 (SAS Inc., Carey, NC). Statistical significance will be defined as $p < .05$. The distribution of continuous variable will be accessed for normality using the Kolmogorov-Smirnov test. Normally distributed continuous variables will be compared using the student's t-test. Non-normally distributed variables will be compared using the Wilcoxon Rank test. Categorical variables will be compared using chi-squared test, unless expected cell counts were <10 , in which case Fischer's exact test will be used.

G. Summarize Knowledge to be Gained:

Rib fractures are common and associated with both acute and chronic pain. This trial will compare two loco-regional treatment modalities currently in use at Denver health to determine the optimal method to decrease post-operative pain and minimize opioid use. Denver Health is a leader in trauma care, including rib fractures. Our team has been produced multiple peer reviewed studies detailing current recommendations for treatment of rib fractures. We will continue to explore novel approaches for trauma patients suffering from rib fracture pain control to further improve patient outcomes and patient satisfaction.

H. References:

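### The SCARF non-inferiority criterion has no fixed postoperative window, so each patient's summary depends on length of stay; if discharge follows recovery, this can shrink a true one-point inferiority

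*Combined protocol and SAP*

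**What the plan says.** IV.A names the outcomes, "Primary outcomes will be pulmonary function and narcotic requirement by each subject", and sets the SCARF schedule: "Pulmonary function will be measured using the Standardized Assessment of Respiratory Function (SCARF) score, measured at 10 am daily". The score runs from 0 to 4, one point for each of pain, spirometry, cough and respiratory rate.

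IV.C ends observation: "Subjects will be followed for 28 days or until discharged from the hospital, whichever comes first". It also allows the catheter to stay in for at most 120 hours.

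IV.F sets the criterion: "Inferiority of liposomal bupivacaine as compared to pain catheter will be defined as median daily SCARF score one point higher". It gives an SD of 1.1 and a total of 34 subjects. The only methods named for comparing the arms are the t-test, the Wilcoxon test, the chi-squared test and Fisher's exact test.

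The protocol does not state the first or last postoperative day that counts, how one patient's daily scores are combined, or what happens to days after discharge.

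**The concern.** Read most directly, the criterion is a median of each patient's daily scores over whatever days were recorded, which means the hospital stay. Stay is itself a post-randomisation outcome. The components of SCARF plausibly bear on fitness to go home, so a patient with worse scores may stay longer. Those extra days come late, when scores have fallen, and they pull that patient's median down. A patient who does well leaves early and is summarised on early days only. If the injection is truly worse, the two arms are then summarised over different parts of the recovery curve, and the difference between them narrows.

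In a superiority trial that would cost power. In a non-inferiority trial it works the other way: an injection that is one point worse can appear comfortably inside the margin.

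**Working it through.** **1. The plan's own figure.** Inputs from IV.F: margin 1, SD 1.1, power 80% (the stated beta of 0.80 read as power), alpha .05, true difference 0.
- Normal formula, one-sided .05: n per arm = 2 × (1.645 + 0.842)² × 1.1² / 1² = 14.96, so 15 per arm, 30 in total.
- Exact t version: 16 per arm, 32 in total.
- Divided by the Wilcoxon efficiency: 16 / 0.955 = 16.75, so 17 per arm, 34 in total.
- With two-sided .05 the t version gives 42.

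The stated 34 therefore fits a one-sided 5% test. The plan does not state the bound, so its use below is an assumption. No follow-up or discharge term enters the formula, so the point does not alter N.

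**2. Simulation inputs.** Taken from the plan: a 0–4 score, SD about 1.1, 17 per arm, margin 1. Everything about recovery and discharge is assumed. Non-inferiority is declared if the upper one-sided 95% t-limit is below 1.
- *Model A* (4,000 trials): mean 2.5 on day 1, falling 0.1–0.3 per day; patient SD 0.9 and residual SD 0.63; discharge possible from day 3 once the score is 1 or less, with a 30–60% chance per day. The true days 1–5 difference is set to 1.0.
- *Model B* (1,500 trials): mean 2.5, falling 0.15–0.35 per day; SDs 0.8 and 0.75; certain discharge at the first score of 1 or less, from day 2 or day 4. The shift is 1 point on the underlying scale.

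**3. Results with recovery-driven discharge.**

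| Summary | A: difference | A: false claims | B: difference | B: false claims |
|---|---|---|---|---|
| Days 1–5, everyone scored | 0.99–1.00 | 4–5% | 0.91–0.96 | 5–8% |
| Median over whole stay | 0.67–0.80 | 20–34% | 0.62–0.70 | 30–47% |
| Mean of observed scores, days 1–5 | 0.95–1.00 | 5–7% | 0.80–0.92 | 8–16% |
| Mean, days 1–5, last score carried forward | 0.99–1.03 | 4–5% | not run | not run |

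The first row is the benchmark. In B it is slightly below 1 because the 0–4 limits compress the shift.

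**4. Hand check of one Model B case** (fall 0.15 per day, discharge from day 2; catheter-arm SD used for both arms; t(.95, 32) = 1.694).
- Days 1–5, everyone scored: difference 0.92, SD 0.91. SE = 0.91 × √(2/17) = 0.312. A claim needs an observed difference below 1 − 1.694 × 0.312 = 0.471. Φ((0.471 − 0.92)/0.312) = 7.5%; simulated 8.1%.
- Whole-stay median: difference 0.65, SD 0.73. SE = 0.250; limit 0.576. Φ((0.576 − 0.65)/0.250) = 38%; simulated 42%.

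**5. What changes if the discharge assumption changes.**
- Discharge unrelated to SCARF: whole-stay median 0.96–1.08 with 3–6% false claims (A); 0.91 with 6% (B). Almost no bias.
- Discharge unrelated to SCARF, with the inferiority lasting only five days: 0.71 with 17% (B). This is dilution by the open window alone.
- Catheter patients held in hospital until at least day 6: whole-stay median 0.83–0.94 with 8–16% (A); 0.87 with 13.5% (B). Among patients still in hospital on day 5 the difference in B is 1.14, larger than the truth. With no true difference, B gives a spurious +0.24 (whole-stay median) and +0.56 (day 5) against the injection.

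**6. Comparing only patients still in hospital.** With recovery-driven discharge, the day-5 difference is 0.81–0.95 against a true 1.03–1.07 in A, and 0.55–0.71 in B.

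**The case against.** The strongest objection is that mechanism and size are assumed. The protocol gives no discharge criteria and no length of stay, and does not link discharge to SCARF. Some simulated stays are long: with the slowest recovery in Model A, the median stay is 19–22 days in the injection arm against 8–11 in the catheter arm, and nothing in the protocol supports such a gap. This stands, and it is why the point is conditional.

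A reader might infer that recovered patients leave the primary comparison altogether. The documents do not support that. Under a per-patient median every randomised patient contributes and only later days are absent. Loss of patients by day arises only if separate daily tests are intended, which IV.F does not say.

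A reader might also take section III, which cites liposomal bupivacaine as "resulting in shorter hospital length of stay", as evidence for the direction. It is not. That result concerns thoracoscopy and thoracotomy patients, and the harmful scenario needs the injection arm to stay longer.

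Finally, most of the loss comes from the open window and little from the absence of a discharge rule. In Model A, observed scores over days 1–5 already recover 0.95–1.00, and carry-forward adds about 0.05 at most. This also stands, and it sets the order of the remedy. Model B's harsher rule shows that some residual bias is possible.

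IV.F refers to a Data Collection Tool that is not in the text available here. It may fix the days recorded, but the criterion in IV.F does not refer to any.

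**Conclusion.** The point holds in conditional form. The criterion as written depends on length of stay. If discharge follows recovery and the injection is truly about one point worse, the whole-stay median shows about 0.6–0.8, and non-inferiority is claimed falsely in about 20–47% of trials where about 5% is intended (5–8% on the full-window benchmark). These figures rest on the two recovery and discharge models above, 17 per arm and a one-sided 5% bound.

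It would go too far to say that the plan is biased toward non-inferiority as a matter of fact. Bias is near zero if discharge is unrelated to SCARF, and a single-day inpatient comparison can be biased against the injection if the catheter delays discharge. The protocol cannot settle which case applies. Because IV.E states that the trial is unblinded, the window should be set before the data are seen.

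**What to change.** In IV.F:
- Base the non-inferiority comparison on one per-patient summary over a fixed early postoperative window, in all randomised patients. The median already named will do; a mean is also acceptable. Days 1–5 is a natural example, since 120 h / 24 = 5 days matches the maximum catheter time. A further run with recovery-driven discharge, using observed days 1–5 only, gave 0.96–0.99 with about 6% false claims for the median and 0.92–0.94 with 8% for the mean.
- Do not base the conclusion on a whole-stay summary, or only on patients still in hospital on a given day.
- For patients discharged inside the window, either use their observed days or carry the last in-hospital score forward. Name one as primary and run the other as a sensitivity analysis.
- Report length of stay by arm.
- If post-discharge days are also scored as 0, note that this is anti-conservative when discharge is unrelated to SCARF (0.86–0.93 for a true difference of about 1, with 7–11% false claims).

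The cost is analysis-plan wording and a few lines of SAS, with no new patients, visits or data. The downsides are that later in-hospital scores become descriptive only, and that carry-forward assumes status at discharge persists for the few remaining days.

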Document Cover Page

Official Title of the Study: A randomized clinical trial of single dose liposomal bupivacaine delivered via VATS intercostal nerve block vs continuous bupivacaine infusion delivered via indwelling subscapular analgesic catheter in patients undergoing surgical stabilization of rib fractures

NCT Number: NCT03305666

Date of Document: April 27, 2017

COMIRB Protocol

COLORADO MULTIPLE INSTITUTIONAL REVIEW BOARD
[name] [contact] [contact]

Protocol #: 17-0685

Project Title: A randomized clinical trial of single dose liposomal bupivacaine delivered via VATS intercostal nerve block vs continuous bupivacaine infusion delivered via indwelling subscapular analgesic catheter in patients undergoing surgical stabilization of rib fractures

Principal Investigator: [name] MD

Version Date: V1 4/27/2017

I. Hypotheses and Specific Aims:

The hypothesis of this clinical trial is that among patients undergoing surgical stabilization of rib fractures (SSRF), liposomal bupivacaine delivered via VATS intercostal nerve block provides comparable analgesia to the pain catheter, as measured by both pulmonary function and narcotic use.

II. Background and Significance:

Rib fractures represent a common injury pattern with high associated morbidity and mortality (1). Effective pain control in both the acute and long term periods remains a challenge (2). Surgical stabilization of rib fractures (SSRF) is now a recommended treatment for patients with severe chest wall injuries (3-5). In addition to stabilization of the chest wall, SSRF offers a unique opportunity to deliver directed, loco-regional anesthesia. Loco-regional anesthesia is a recognized, essential component of multi-modal anesthesia for patients with rib fractures in order to both decrease pain and minimize the use of opioids and their associated side effects (6, 7).

Delivery options for loco-regional anesthesia to patients with rib fractures share in common the intention of anesthetizing the intercostal nerves. Moving from the spinal cord distally, modalities include thoracic epidural catheters, paravertebral blocks or catheters, and rib blocks. Although rib blocks may be accomplished via a variety of techniques, the two most common intra-operative techniques are video-assisted thoracoscopic surgery (VATS) intercostal nerve blocks [Figure 1] and indwelling, subscapular catheters (Figure 2).

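### The trial is declared non-inferiority with a one-point SCARF margin, but no planned analysis tests that margin and no rule says what result establishes non-inferiority

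*Combined protocol and SAP*

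**What the plan says.** The hypothesis (Section I, repeated in Section II) is that liposomal bupivacaine "provides comparable analgesia to the pain catheter, as measured by both pulmonary function and narcotic use". Section IV.A makes both measures primary: "Primary outcomes will be pulmonary function and narcotic requirement by each subject". Section IV.C names the design: "This is a non-inferiority, randomized clinical trial".

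Section IV.F opens with the margin: "Inferiority of liposomal bupivacaine as compared to pain catheter will be defined as median daily SCARF score one point higher". It then gives an SD of 1.1 and the sample size: "Using beta = 0.80 and alpha = .05, this returns a total sample size of 34 subjects". The margin does not appear again.

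The analysis paragraph sets significance at p < .05 without stating sidedness. It continues: "The distribution of continuous variable will be accessed for normality using the Kolmogorov-Smirnov test". Variables judged normal go to Student's t-test. For the rest: "Non-normally distributed variables will be compared using the Wilcoxon Rank test". Categorical variables go to chi-squared or Fisher's exact test. These instructions cover continuous and categorical variables in general; none is specific to SCARF or to the non-inferiority question.

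**The concern.** A t-test or Wilcoxon test with no stated shift asks whether the arms differ at all. A non-inferiority trial asks whether a deficit as large as the margin can be ruled out. Failing to find a difference among 34 patients does not rule out a one-point deficit.

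The only criterion in the text, a median one point higher, is worded as a comparison of observed values and ignores sampling error. Nothing says which result would establish non-inferiority. For narcotic use there is not even a margin, so half of the hypothesis has no non-inferiority criterion.

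The trial is open-label (Section IV.E), so leaving the criterion unwritten allows it to be chosen once results are visible. At stake is whether the headline claim of comparable analgesia carries any controlled error rate.

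**Working it through.** **Inputs.** From IV.F: margin 1 point, SD 1.1, alpha .05 (sidedness not stated), power 0.80 (the plan writes this as beta), total N = 34. Assumptions: 17 per arm (IV.C describes a random 0/1 draw and states no ratio), SD 1.1 as the SD of the per-patient summary, normal model, mean difference standing in for the median difference, no dropout.

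**1. Reproduce N = 34.** Normal approximation, true difference 0: n per arm = 2 × [1.1 × (z_alpha + z_power) / 1]².
- One-sided .05: 2 × [1.1 × (1.645 + 0.842)]² = 14.96, so 15 per arm, N = 30.
- Two-sided .05: 2 × [1.1 × (1.960 + 0.842)]² = 18.99, so 19 per arm, N = 38.

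With the noncentral t, one-sided .05 needs 16 per arm (N = 32). Dividing by the Wilcoxon efficiency, 16 / 0.955 = 16.8, gives 17 per arm (N = 34). Two-sided .05 needs 40–42 (20 per arm gives almost exactly 80%), or 44 when 21 per arm is adjusted for Wilcoxon. Among the variants tried, 34 fits only one-sided .05, the sizing of a margin test at that level.

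**2. What a margin test requires.** SE = 1.1 × √(2/17) = 0.377, with 32 degrees of freedom.
- 90% CI half-width: 1.694 × 0.377 = 0.639. Non-inferiority needs an observed difference below 1 − 0.639 = 0.36.
- Two-sided significance at .05 needs |difference| > 2.037 × 0.377 = 0.77.

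Observed differences of about 0.36 to 0.77 are neither significant nor non-inferior. With the SD estimated from the data, this outcome has probability about 15% if the true difference is 0 and 39% if it is 0.5. If the difference test is one-sided in the harm direction, the band is 0.36 to 0.64 and the probabilities are about 12% and 27%.

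**3. If p ≥ .05 were read as comparable (an inference; the plan does not say so).** At a true difference of 1, the noncentrality is 1 / 0.377 = 2.65.
- Two-sided: P(p ≥ .05) = 27.1%.
- One-sided: P(p ≥ .05) = 17.1%.
- Margin test at one-sided .05: 5%.

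If 1.1 is instead a single-day SD and k daily scores are averaged, the SD becomes 1.1 × √[(1 + (k − 1)ρ)/k]. For k = 3–5 and ρ = 0.3–0.7 (assumed) this is 0.73–0.98, and the two-sided figure falls to 3–18%.

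**4. If an observed median difference below 1 were read as not inferior.** For a continuous symmetric summary, a treatment exactly one point worse is passed 50% of the time. As an illustration, take one integer score per patient (a normal with SD 1.1, rounded and clipped to 0–4). The false-pass rate is then about 12–25%, and two identical arms are called inferior about equally often.

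**5. Power of the 90% CI rule at 17 per arm.** 83% at true difference 0, 62% at 0.25, 36% at 0.5. At one-sided .025 (95% CI), power at 0 is 72.9%.

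**The case against.** The inferiority sentence opens the Data Analysis Plan and is worded as a definition, so it could be taken as the decision rule. A t-test or Wilcoxon test can also be run against a one-point shift, and the sample size suggests that a margin test was intended. The plan never says that non-significance means comparability, so the 27% is conditional; at the sidedness that the sample size implies it is 17%. Inconclusive results are not caused by the plan: under the CI rule, non-inferiority is still not shown in about 17% of trials at true difference 0 and 64% at 0.5. The integer-score figures rest on a score distribution that the documents do not give.

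Much of this is fair as qualification. The error rates are conditional, both sidednesses belong in the account, and the integer-score figures are illustrative. The CI rule does not make inconclusive results rarer; it says how to report them. None of this supplies the missing rule. Read as a decision rule, the definition is a point-estimate criterion without error control. A shifted null is possible but is not written. A sample size that fits a one-sided margin test makes its absence from the analysis more conspicuous.

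**Conclusion.** The concern holds, and the plan must be corrected before analysis. No section gives a confidence-interval rule, a shifted null or any other test of the one-point margin, and narcotic use has no margin at all. This part does not depend on any calculation.

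The size of the harm depends on how the gap would be filled: a false-claim rate of 27% (two-sided) or 17% (one-sided) if non-significance were taken as comparability, 3–18% two-sided if 1.1 is a single-day SD, and 50% under the bare point-estimate reading of a continuous summary. The figures rest on 17 per arm and the normal model; the 27% and 17% also take 1.1 as the per-patient SD. The comparator is 5% for a margin test at one-sided .05.

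**What to change.** In IV.F, make these changes:
- **Summary.** Prespecify one SCARF value per patient, for example the mean of the 10 am scores over a fixed postoperative window that is the same in both arms.
- **Rule.** State that non-inferiority on SCARF is concluded only if the upper limit of the two-sided 90% CI (one-sided alpha .05) for liposomal minus catheter is below 1.0, and that p ≥ .05 from a difference test is not evidence of comparability.
- **Method.** Name one, and do not let the Kolmogorov-Smirnov test choose it. Use a mean difference if the sponsor restates the margin on the mean scale, which is a change from the stated median. If a rank method is kept, use a Hodges-Lehmann shift with its CI, applied to per-patient averages. In simulated 0–4 scores with one score per patient, Hodges-Lehmann power at zero difference was only 35–42%, against 86–90% for the mean difference.
- **Narcotic use.** Either prespecify a margin with the same kind of rule, or limit the non-inferiority conclusion to SCARF and label narcotic use as a difference comparison.

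A per-protocol repeat and a follow-on superiority test are optional.

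The cost at one-sided .05 is wording only, with no extra data or patients and about 83% power at zero difference. The sponsor still has to decide the summary window and the margin scale. If one-sided .025 is preferred, 34 patients give 72.9% power and about 40–42 are needed for 80%. A narcotic margin would need its own power check.
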